5.3.5 Evaluable and Non-Evaluable Whole Blood Collections

Collected whole blood's evaliability status per protocol definition (see section 5.3.5.1) will determine whether these data are included within the data set that will be analyzed towards study endpoints. Blood donations deemed unevaluable per protocol definition will necessitate whole blood sample replacement obtained from alternate evaluable study donors such that intended population targets are maintained.

5.3.5.1 Definition of Non-Evaluable Whole Blood Collection

Study Protocol

Protocol #: CLIN-0001

Date: 28 Nov 2017

Clinical Investigation to Evaluate the New Health Sciences Hemanext® Oxygen Reduction System for Leukoreduced Red Blood Cells with CP2D Anticoagulant and AS-3 Additive - Pivotal Trial

Page 18 of 65

Each of the following issues or occurrences defines a non-evaluable whole blood collection. Partial data sets from donors who provide data and/or blood donations will be entered into the database and reported within descriptive statistics as outlined within the study's statistical analysis plan (SAP).

- **TTD:** Data/analyses resulting from blood acquired from donors who are subsequently determined to test positive for TTD will result in a determination of non-evaluability and will not be included within study endpoint analyses. Upon TTD positive determination, further analyses of the blood will cease, the study donor will be notified via site-respective procedures, and any collected data will be reported as descriptive statistics.
- **Slow Collection:** Any whole blood collection taking longer than 15 minutes to complete will be considered a slow collection and will be defined by the point that the cannula on the respective system's Donor Line is broken to initiate blood flow into the Donor Bag until the Donor Line is clamped to cease blood flow to the Donor Bag at the end of collection. All whole blood units resulting from a slow collection will be non-evaluable. Information/data from study donors from whom the collection is slow per this definition will only be included within the demographics section of the descriptive statistics.
- **Incomplete Collection:** Upon collection of the full unit and prior to any sampling, filtration or processing, any collection that is stopped prior to reaching the 500 ± 50 mL acceptable volume range will be considered unevaluable. With the exception of descriptive statistics, data resulting from incomplete collection donations will not be included in study-related analyses.
- **Protocol Deviation:** Any procedural protocol deviation that the PI and/or sponsor determine(s) has the potential to impact (both positively and negatively) any acceptance criteria, study endpoint and/or analytical study-critical outcomes will result in a determination of non-evaluability. Procedural protocol deviations must be documented within the eCRFs and all deviations that compromise data validity (i.e., one that impacts evaluability) must be reported to the sponsor within 24 hours (see section 9.3). Examples of protocol deviation that have the potential to impact study outcomes include but are not limited to the following: (1) storage deviation (e.g., electrical outage and unknown storage conditions, unit left out of refrigeration for >30 minutes, sample frozen vs. refrigerated, etc.), (2) incorrect mixing/agitation (e.g., unit dropped from height, unit inappropriately mixed prior to sampling, excess sample drawn into syringe and quickly re-injected back into unit, etc.), (3) other deviation (e.g., incorrect

Study Protocol

Clinical Investigation to Evaluate the New Health Sciences Hemanext® Oxygen Reduction System for Leukoreduced Red Blood Cells with CP2D Anticoagulant and AS-3 Additive - Pivotal Trial

Protocol #: CLIN-0001

Date: 28 Nov 2017

Page 19 of 65

centrifuge speed/duration, other)). Deviations must further be communicated to the respective IRB per local regulations.

- **Sickle Cell Trait:** Any whole blood unit in the study from a sickle cell trait (SCT) positive study donor will be excluded.
- **Grossly Lipemic Specimens:** Any whole blood unit grossly evaluated (per visual inspection) as lipemic will be non-evaluable relative to only the RBC hemolysis endpoint at Day 42. Any units in question will be reviewed by the PI or designee and if considered non-evaluable, the unit will be removed from the study, and the study donor may be replaced.
- **Positive Bacterial Culture:** This evaluability determination pertains only to study donors who participate in the in vivo portion of the study. Should the outcome of the pre-infusion bacterial culture (see section 6.2.16.11) indicate that the stored LRRBCs are '+' for bacteria, then the unit will be discarded. As a result, the study donor and his/her unit of blood will be non-evaluable and the study donor may be replaced.

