5.4 Statistical Analysis Plan

The data from this study will be analyzed to determine whether the primary endpoints and study acceptance criteria (as recommended by FDA and as listed in section 5.2) were met.

In order to assure that 95% confidence in 95% reliability of the of the lower confidence level of the units meet the acceptance criteria for the primary endpoints, the sample size shall be:

- Ninety-three (93) evaluable procedures in which no more than one (1) failure occurs against the acceptance criteria for the primary endpoints.

Secondary analyses, such as differences in populations by site and comparisons between arms, will be described in more detail within the statistical analysis plan. This formal SAP will be developed in conjunction but separately from this protocol, and filed within the trial master file.

The following, at a minimum, will be presented using descriptive statistics:

- **Donor Disposition:** All data on all study donors enrolled in trial including data identified as evaluable and non-evaluable donations will be presented.
- **Demographics:** Age, gender, weight, height, ethnicity and race will be provided for all study donors enrolled in the trial for both evaluable and non-evaluable donations. A comparison to census data will be performed in the final report.
- **Collection procedure-related data:** Collection duration and ambient temperatures will be provided for both evaluable and non-evaluable donations.

Study Protocol

Clinical Investigation to Evaluate the New Health Sciences Hemanext® Oxygen Reduction System for Leukoreduced Red Blood Cells with CP2D Anticoagulant and AS-3 Additive - Pivotal Trial

Protocol #: CLIN-0001

Date: 28 Nov 2017

Page 20 of 65

- **Filtration & processing procedure-related data:** Temperature, head height, filtration time, filter time, filter weight, and final collection volumes will be provided for evaluable and non-evaluable donations.
- **Laboratory data:** Laboratory data will be provided for evaluable and non-evaluable donations (if applicable). Other than the endpoints detailed in the acceptance criteria, the laboratory data will be presented for information only.
- **Adverse events:** Expected, unexpected and serious adverse events will be reported for all enrolled study donors.

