10.0 Data Use**10.1 Test Report**

A final report will be prepared by NHSi and be reviewed by the study sites. This final report will include data reported on all study donors enrolled including cases where they

Study Protocol

Clinical Investigation to Evaluate the New Health Sciences Hemanext® Oxygen Reduction System for Leukoreduced Red Blood Cells with CP2D Anticoagulant and AS-3 Additive - Pivotal Trial

Protocol #: CLIN-0001

Date: 28 Nov 2017

Page 51 of 65

are excluded from the total evaluable study donors. This report will be made available to all persons responsible for the conduct of the study.

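### The slow-collection rule limits reporting to demographics, which contradicts the adverse event and collection-duration summaries in section 5.4

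*Combined protocol and SAP*

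**What the plan says.** The slow-collection bullet in section 5.3.5.1 has three parts:

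- The threshold: "Any whole blood collection taking longer than 15 minutes to complete will be considered a slow collection".
- The consequence for the unit: "All whole blood units resulting from a slow collection will be non-evaluable".
- The reporting rule, which is worded for the donor: data from study donors with a slow collection "will only be included within the demographics section of the descriptive statistics".

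The opening of the same section says that partial data sets from non-evaluable collections go into the database and are described as the SAP sets out. The neighbouring bullets on transfusion-transmitted disease and on incomplete collection keep descriptive reporting and do not confine it to demographics.

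Section 5.4 sets out the minimum descriptive outputs. Demographics means age, gender, weight, height, ethnicity and race. Two other items stand apart from it:

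- On collection: "Collection duration and ambient temperatures will be provided for both evaluable and non-evaluable donations".
- On safety: "Expected, unexpected and serious adverse events will be reported for all enrolled study donors".

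Section 6.2.2 counts everyone who has signed consent as enrolled, evaluable or not. Section 10.1 opens the reporting scope in the same way ("This final report will include data reported on all study donors enrolled including cases where they") and goes on to cover donors left out of the evaluable total.

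**The concern.** Adverse events and collection duration are not demographic items, so the word *only* in the bullet excludes what section 5.4 promises. A programmer building the tables could follow either sentence and be in line with the protocol.

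Three things depend on which sentence is followed:

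- **Safety summary.** Donors would leave the adverse event table because of how their collection went, which makes the table selective. Section 7.2.1 appoints no data safety monitoring board, so the final report is the main pooled view of safety that the documents describe.
- **Duration summary.** The collections that the 15-minute rule is meant to identify would be missing from the table that describes collection time.
- **The other donation.** Each donor gives two units. The bullet moves from units to study donors between its second and third parts, so it does not settle whether a normally collected unit from the same donor is described.

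**Working it through.** **1. The plan's own figure.** Sections 5.3.1 and 5.4 require 93 evaluable procedures with at most one failure, for 95% confidence in 95% reliability. The check is the chance of passing when true reliability is exactly 0.95:

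P(at least n − 1 successes) = 0.95^n + n × 0.05 × 0.95^(n−1)

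- n = 92 gives 0.05214, above 0.05.
- n = 93 gives 0.04998, below 0.05.

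So 93 is the smallest n that works. The exact one-sided 95% lower limit for 92 of 93 is 0.950006. The figure reproduces. It does not bear on this point, because slow collections are outside the endpoint analysis whichever sentence governs reporting.

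**2. The passages side by side, for a donor with a slow collection.**

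| Item | Slow-collection bullet, 5.3.5.1 | Section 5.4 |
|---|---|---|
| Demographics | Reported | Reported |
| Adverse events | Not reported | Reported for everyone enrolled |
| Collection duration | Not reported | Reported, evaluable or not |
| Disposition | Not reported | All data on everyone enrolled |
| Laboratory data, slow unit | Not reported | Reported if applicable |
| Laboratory data, other unit | Unclear | Reported |

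The adverse event and duration rows are direct contradictions. The disposition row points the same way. The laboratory rows are softer: section 5.4 qualifies non-evaluable laboratory data, and the bullet's reach to the other unit is uncertain.

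**3. Could the donor fall outside the section 5.4 populations?** No. Under section 6.2.2 a slow-collection donor has consented and is therefore enrolled. Under section 5.3.5.1 the donation is non-evaluable, and section 5.4 names non-evaluable donations for the duration output.

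**4. Effect on the duration table.** By definition every slow collection exceeds 15 minutes, so leaving them out leaves no value above 15 minutes on that clock. The bullet times from breaking the cannula to clamping the donor line. Section 6.2.16.3 records needle-in and needle-out times. A summary built from the recorded times would therefore be cut at about 15 minutes, not exactly there.

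**5. Number affected.** Planned collections run from 2 × 93 = 186 to 2 × 100 = 200. Each percentage point of slow collections would be about 2 collections (186 × 0.01 = 1.86; 200 × 0.01 = 2). The documents give no rate, so the count cannot be taken further.

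**The case against.** The strongest reply is that nothing need be lost. Section 5.4 still promises these outputs, as a minimum. Section 10.1 covers excluded donors. Adverse events are documented at collection (section 6.2.16.3) and reported to the sponsor (sections 7.2.1 and 7.2.2.2) regardless of evaluability. A separate formal SAP is to follow, and it may settle the matter. All of this stands, and it limits the point to a conflict over reporting. It does not remove the conflict: no sentence gives section 5.4 precedence, the bullet is the more specific rule, and the separate SAP is not among the documents, so whether it resolves the conflict cannot be checked.

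A reader might infer more than the text supports in four ways:

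- **That the rule certainly deletes adverse events and long durations.** This follows only if the bullet overrides section 5.4, and nothing says that it does.
- **That the donor's other unit is certainly dropped.** Section 5.3.5 deals with collections, and the last sentence can fairly be read as covering data from the slow collection alone. The donor-wide reading is possible but not compelled.
- **That a test unit could be removed after its result is known, when a test-first donor has a slow second collection.** Section 6.2.13 has hemolysis batch-tested, so Day 42 sampling does not show that the result was known by the second donation. The rule is a fixed time threshold with no discretion described. Section 5.3.2 already requires two completed Day 42 periods for a donor to be evaluable.
- **That phlebotomy injuries concentrate in slow collections.** Section 7.2.2.5 lists hematoma, arterial puncture and nerve injury as expected events but does not link them to collection time.

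**Conclusion.** The contradiction is real and lies in the current text. On adverse events and collection duration, section 5.3.5.1 and section 5.4 give opposite instructions for the same donors, and the bullet also departs from its section's opening. On the donor's other unit, the wording is ambiguous rather than contradictory.

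The size is modest. The primary endpoints and the rule of 93 with at most one failure do not change, and the underlying data are still captured. What is open is whether the safety and collection summaries cover everyone they are said to cover. The conclusion rests on reading *only* in its ordinary sense and on section 5.4's own list of what demographics contains. It needs no assumed slow-collection rate.

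**What to change.** Replace the last sentence of the slow-collection bullet with a unit-level rule, for example:

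*The unit from a slow collection is excluded from the endpoint analyses. Its collection data and the donor's adverse events are reported as section 5.4 provides. Data from the donor's other unit are reported descriptively.*

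The separate SAP should carry the same rule, and it should be settled before tables are programmed. The cost is a short text change. Collection times and adverse events are already recorded under section 6.2.16.3, so no new procedure or data item is needed, and the sample size is unchanged.

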5.2 Study Primary Endpoints and Acceptance Criteria

The primary endpoints that will be evaluated in this clinical trial are RBC mass recovery, hemolysis and 24-hour in vivo red cell recovery. The endpoint-associated study acceptance criteria are listed below:

- A one-sided 95% lower confidence limit for the true proportion of packed RBC units with hemolysis at day 42 of < 1% is > 95%.
- The mean 24-hour, post-transfusion, in vivo red cell recovery of at least 75% with a standard deviation of $\leq 9\%$, and the lower limit of a one-sided 95% confidence interval for the population proportion of successes is $\geq 70\%$.
- Red Blood cell recovery $\geq 85\%$; with 95% confidence that at least 95% of units are $\geq 85\%$.

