5.3 Donor/Data Criteria**5.3.1 Sample Size**

The sample sizes described within the protocol were selected to demonstrate meeting study primary endpoints that conform to the FDA's 95-95 rule (95% confidence and 95% reliability). For successful endpoint outcomes, the study requires meeting the acceptance criteria in 92 of 93 test units per test condition. Therefore, 93 evaluable study donors will complete the study. In the event of two (2) donors/units with unmet acceptance criterion occurring out of ninety-three (93) evaluable procedures (i.e., within one or more study arm(s) for one or more acceptance criteria/primary endpoints), the study will be discontinued.

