5.3.2 Intended Study Enrollment

Definitions:

- **Study Donor:** an individual who has signed the informed consent form and is enrolled in the study.
- **Evaluable Study Donor:** an individual who is enrolled in the study, meets the inclusion criteria, and completes two Day 42 test periods.

This clinical trial requires enrolling a total of 93 evaluable study donors. However, due to the study design which incorporates a 2x2 crossover and the in vivo RBC recovery and survival substudy, the study will purposely enroll up to 100 study donors to account for study withdrawal, loss to follow-up and/or study donors who meet study criteria for the first donation of the crossover, but fail to meet study criteria for the second donation.

The study sites will make efforts to balance gender during screening.

Once enrolled, if a study donor's status should change from evaluable to non-evaluable per protocol definitions (see section 5.3.5), or if the study donor should discontinue follow-up (e.g., either voluntarily withdraw from the trial or become

Study Protocol

Clinical Investigation to Evaluate the New Health Sciences Hemanext® Oxygen Reduction System for Leukoreduced Red Blood Cells with CP2D Anticoagulant and AS-3 Additive - Pivotal Trial

Protocol #: CLIN-0001

Date: 28 Nov 2017

Page 15 of 65

lost to follow-up), then that study donor may be replaced in order to maintain intended study enrollment goals. Such replacement would increase the total number of enrolled study donors, but maintain the final number of evaluable study donors.

In instances where up to 100 study donors have been enrolled and all have undergone their first donation, consecutive donors will return for their second donation until a complete set of 93 matched data pairs have been obtained for both in vitro and, when applicable, in vivo parameters. As a result, it is possible that a study donor who donates an evaluable unit of whole blood will not be asked to return to provide a second unit of whole blood in instances where a complete data set has already been ascertained within the relative study arm.

Site A is not participating in enrolling donors for the in vivo cohort of the study. Site A will target enrollment of 40 evaluable donors for in vitro testing only. Site H will target enrollment 46 evaluable donors for in vitro testing of which 14 will also be enrolled for the cohort of in vivo testing. Site B target enrollment 14 evaluable donors for both in vivo and in vitro testing.

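### The lipemic-unit rule contradicts itself on scope and on replacement, and does not require the exclusion decision to precede the Day 42 hemolysis result

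*Combined protocol and SAP*

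**What the plan says.** **Lipemia rule (section 5.3.5.1, Grossly Lipemic Specimens).** A unit judged lipemic by eye is "non-evaluable relative to only the RBC hemolysis endpoint at Day 42". Doubtful units go to the PI or a designee, and if one is considered non-evaluable, "the unit will be removed from the study, and the study donor may be replaced". The bullet gives no threshold and no deadline for that review.

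**Replacement and evaluability.**
- Section 5.3.5 makes replacement compulsory for donations found unevaluable, so that population targets hold.
- Section 5.3.2 defines an evaluable donor by enrollment, inclusion criteria and completion of both Day 42 testing periods. It does not mention a usable hemolysis result. It continues second donations until 93 matched pairs exist, and "the study will purposely enroll up to 100 study donors to account for study withdrawal, loss to follow-up" among other reasons.
- Section 5.3.4 requires replacement of a withdrawn donor whenever data needed for the acceptance criteria are incomplete.

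**Decision rule.**
- Section 5.2 sets the hemolysis criterion as a one-sided 95% lower confidence limit above 95% for the proportion of units below 1% hemolysis at Day 42. RBC recovery and 24-hour in vivo recovery are also primary endpoints.
- Section 5.3.1 says "the study requires meeting the acceptance criteria in 92 of 93 test units per test condition", and a second failure discontinues the study.
- Section 5.4 asks for "Ninety-three (93) evaluable procedures in which no more than one (1) failure occurs against the acceptance criteria for the primary endpoints".

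**Who sees the results.** Under section 6.2.13 the sites work out whether hemolysis meets the criterion and quickly tell the sponsor when values look out of range.

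**The concern.** Three things are unsettled in a rule that decides membership of a primary analysis set.

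1. **Scope.** The two sentences produce different data sets for RBC recovery and, for in vivo donors, for 24-hour recovery. A site cannot follow both. Lipemia is presented as a reason to distrust the hemolysis result, yet the second sentence would let it remove a recovery success or failure as well. The in vivo cohort is small (24 to 28 in Table 2), so each unit lost there matters.
2. **Number.** The one-failure allowance works only if the hemolysis set itself reaches 93. No section states 93 hemolysis-evaluable units.
3. **Timing.** The review is visual and undated, and the people making it may already know the hemolysis value. With one failure allowed and two ending the study, reclassifying a single unit can decide the outcome.

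**Working it through.** **Inputs.** Required reliability 0.95 and one-sided confidence 95% (sections 5.2 and 5.3.1); n = 93 with at most one failure (sections 5.3.1 and 5.4). The documents name no interval method. The exact binomial is used because it reproduces the plan's 93.

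**Step 1: reproduce the plan's figure.** With X failures among n units and a true failure rate of 0.05, a rule allowing one failure needs

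P(X ≤ 1) = 0.95^n + n × 0.05 × 0.95^(n−1) ≤ 0.05.

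- n = 93: 0.008478 + 4.65 × 0.008924 = 0.04998, which meets the bound.
- n = 92: 0.008924 + 4.60 × 0.009394 = 0.05214, which does not.

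So 93 is the smallest n that allows one failure. The corresponding minimum is 59 for no failures and 124 for two.

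**Step 2: the same result as a confidence limit.** The exact (Clopper-Pearson) one-sided 95% lower limit with f failures is the 5th percentile of a Beta(n − f, f + 1) distribution.

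| Units | Failures | Lower limit | Above 95%? |
|---|---|---|---|
| 93 | 1 | 95.0006% | yes |
| 92 | 1 | 94.947% | no |
| 92 | 0 | 96.80% | yes |

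**Step 3: what one missing hemolysis result would cost.** At 92 units the exact criterion permits no failures. The documents give no true success rate p, so the values below are assumptions. The pass probability is p^93 + 93(1 − p)p^92 at 93 units and p^92 at 92 units.

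| Assumed p | At least 92 of 93 | 92 of 92 |
|---|---|---|
| 99% | 76.2% | 39.7% |
| 99.5% | 92.1% | 63.1% |
| 99.8% | 98.5% | 83.2% |

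**Step 4: bound on a result-dependent exclusion.** Suppose the true reliability is exactly 95%, exactly two of 93 units fail, one of them is always declared lipemic, and its replacement passes with probability 0.95.

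- P(X = 2 | 93) = 4278 × 0.05² × 0.95^91 = 4278 × 0.0025 × 0.009394 = 0.1005.
- False-pass risk = 0.04998 + 0.1005 × 0.95 = 0.1454, against 0.04998 without the exclusion.

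Steps 3 and 4 are alternatives: in Step 3 the unit is not replaced and in Step 4 it is. They do not add up.

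**The case against.** **The set is meant to be 93.** A reader might infer from the optional replacement that the hemolysis set will drop to 92 and that the trial could then pass wrongly on one failure. The documents do not support that. Section 5.3.5 compels replacement, sections 5.3.1 and 5.4 require 93 evaluable procedures, and section 5.3.2 runs to 93 matched pairs with up to 100 donors enrolled. The optional wording can also be read as applying to the donor while section 5.3.5 governs the blood sample. The one-failure allowance is tied to 93, and the section 5.2 criterion is the limit itself, so under the exact method 91/92 would fail. Even if the allowance were carried over to 92, the false-pass risk would move only from 5.00% to 5.21%. Wilson and Jeffreys limits at 91/92 are 95.27% and 95.83%, so the failure there depends on the exact method.

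This largely stands. What remains is that a unit set aside for one endpoint is not clearly an unevaluable donation under section 5.3.5, and that the section 5.3.2 donor definition does not ask for a hemolysis result.

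**The lipemia call may be early.** The bullet speaks of a whole blood unit, and whole blood is filtered and separated on the day of collection (section 6.2.16). Reference plasma is frozen before filtration (section 6.2.16.4) and might support a later check. That makes an early call plausible, but nothing dates the PI review or keeps it blind. The detailed data lists in section 6.2.16 have no lipemia item.

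**Data are not lost.** Partial data are still reported descriptively (sections 5.3.5.1 and 5.4). This is correct: the loss is from the endpoint analyses only.

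**Details may be elsewhere.** Section 5.4 refers to a separately filed SAP, which is not in the documents reviewed and may define the analysis sets.

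**Conclusion.** The point holds as an inconsistency among sections 5.3.2, 5.3.5 and 5.3.5.1, together with an undated exclusion decision. The contradiction on scope is plain in the text and affects which units enter two other primary endpoints.

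On number, the plan intends 93 and its arithmetic is right. Because there is no margin below 93 under the exact limit, the wording should guarantee that figure for the hemolysis set and not only for donors.

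On timing, the increase from 5.0% to 14.5% is a ceiling for one exclusion. It assumes a true reliability of exactly 95% and that a failing unit is always declared lipemic whatever its appearance. A reader might take it as an expected error rate or as a suggestion of misconduct. The documents give no lipemia frequency and support neither reading. The figure shows only how much could turn on one undated visual judgement.

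**What to change.** Reconcile sections 5.3.2, 5.3.5 and 5.3.5.1 as follows.

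1. State that a grossly lipemic unit is excluded from the Day 42 hemolysis endpoint only, and that its RBC recovery and any in vivo data stay in the endpoint analyses.
2. Bring the optional replacement wording into line with section 5.3.5, and state that the hemolysis analysis requires 93 hemolysis-evaluable test units.
3. Require the lipemia determination to be recorded, with date and time, before the Day 42 supernatant hemoglobin is known, or by someone blind to it. Add the item to the data collection lists.

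These are wording changes plus one data field. The downside is an occasional extra replacement donation.
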